9.9. Premature Termination of the Study

The Sponsor reserves the right to stop the study at any time on the basis of new information regarding safety or efficacy (e.g., discovery of an unexpected, significant or unacceptable risk to the patients enrolled in the study), or if study progress is unsatisfactory (e.g., failure to enrol patients at an acceptable rate), or for other valid reasons (e.g., Sponsor decides to suspend or discontinue development of the drug). After such a decision is made, the Investigator must inform all on-study patients within 1 week. All delivered study materials must be collected and all eCRF pages completed to the extent possible.

9.10. Confidentiality

All study findings and documents will be regarded as confidential. The Investigator and members of their research team must not disclose any information without prior written approval from the Sponsor.

The anonymity of participating patients must be maintained. Only patient number (code) will be recorded in the eCRF. Documents that identify the patient will be coded by using only patient number codes.

9.11. Other Ethical and Regulatory Issues

If a significant safety issue is identified, either from an individual case report or review of aggregate data, then the Sponsor will issue prompt notification to all parties regulatory authorities, Investigators and IEC/ EC.

A significant safety issue is one that has a significant impact on the course of the clinical study or programme (including the potential for suspension of the development programme or amendments to protocols) or warrants immediate update of informed consent.

9.12. Publication Policy

Any manuscript, abstract or other publication or presentation of results or information arising in connection with the study (including any ancillary study involving study patients) must be prepared in conjunction with the study Sponsor and must be submitted to the Sponsor for review and comment at least 45 days prior to submission for publication or presentation. No single centre or groups of centres may publish individually. The Sponsor's comments on the proposed publication shall be considered in good faith by the authors. The Sponsor may delay such submission by a maximum of 90 days if it reasonably believes that publication of results may compromise its intellectual property rights or may insist that such information or data is removed from the proposed publication. Publication of the results will not include confidential information without the permission of the Sponsor.

The original eCRF pages and all data generated during the study under this protocol will become the property of the Sponsor.

The Sponsor may announce quality-assured summary data in order to comply with the requirements of financial regulatory authorities, while ensuring so far as possible that such announcements will not compromise the Investigators' ability to publish the data in appropriate scientific forums.

 19.4 Data listing plan24

1 Abbreviations

AE	Adverse event
ANOVA	Analysis of variance
ATC	Anatomical Therapeutic Chemical
FAS-E	Full analysis set for efficacy
FAS-S	Full analysis set for safety
IAP	Intra-abdominal pressure
ICU	Intensive care unit
MedDRA	Medical dictionary of regulatory authorities
mRS	Modified ranking scale
NAb	Neutralizing antibody
PD	Pharmacodynamics
PIM	Potential Inflammatory Markers
PPS	Per protocol set
SD	Standard deviation
SAE	Serious adverse event
SOFA	Sequential organ failure assessment
TEAE	Treatment emergent adverse event
VFD	Ventilator free day

2 General remark

This SAP version further details the SAP dated 17.6.2019, which was generated before performing the Interim analysis for the 35 evaluable patients. Study was discontinued after the Interim analysis. The earlier version of the SAP concentrated on the primary analyses and this version will entail all planned analyses. The analysis plans concerning the primary analyses are not changed from the previous version.

As the study was discontinued, analyses described here, will be performed on the available data gathered thus far.

3 Study objective(s)

The primary objective of this study is to evaluate the safety and the efficacy of FP-1201-lyo over placebo on all-cause mortality at study day 30; D30 (30 days from the first dose of study medication).

The secondary objectives of this study are

1. To evaluate the efficacy of FP-1201-lyo treatment by assessing short term outcomes (D30) and mid-term outcomes (D90 [3 months])
2. To evaluate the safety and tolerability of FP-1201-lyo treatment

3. To evaluate the pharmacodynamics (PD) of FP-1201-lyo
4. To evaluate the Tentative Disease Specific Marker CD73 and Potential Inflammatory Markers (PIM) IL-6 and HGF
5. To evaluate neutralizing antibodies against IFN beta-1a (NAbs)

4 Design and type of the study

This is a multicentre, randomised, double-blind, Phase II, parallel group comparison study of the efficacy and safety of FP-1201-lyo compared to placebo in patients surviving emergency open surgery for an infra-renal ruptured abdominal aortic aneurysm. Both treatment groups will receive standard supportive care.

Patients will receive 10 µg FP-1201-lyo or placebo intravenously as a bolus injection once every 24 hours. The maximum duration of treatment will be 6 days. Treatment may be discontinued before 6 days if the patient's condition improves beyond the need for ICU treatment and if, in the opinion of the Investigator, the patient would likely not benefit from continuation of treatment.

With an estimated screening failure rate of approximately 15%, a maximum of 180 patients were planned to be consented and entered into the study in order to randomise and initiate treatment of 152 patients.

Study was discontinued after an Interim analysis.

5 Study variables

The following variables will be evaluated

The demographic and baseline variables

Gender, age at entry, race, weight (predicted or actual), height, medical history, concomitant medications/therapies, major surgical outcomes affecting patient and pregnancy test (females of child bearing potential, and peri procedural information (duration of the surgical procedure for RAAA, total clamping time, total bleeding volume, total volume substitution, total blood substitution, total red blood cells substitution, total platelets substitution, total crystalloids substitution and total diuresis volume during procedure and recycling of blood during surgery (yes/no)).

The primary efficacy outcome variable

- All-cause mortality at D30

The secondary efficacy outcome variables

- All-cause mortality at D90 (3 months)
- Number of ventilator free days (VFDs) at D30
- Number of days receiving haemodialysis at D30 and D90
- Number of organ failure free days up to D30 by means of the SOFA score
- Prevalence of abdominal compartment syndrome, i.e. intra-abdominal pressure (IAP) between treatment groups
- Neutralizing antibodies against IFN beta (NAbs) in whole blood samples up to D30

- Disability on D90 measured by modified ranking scale (mRS)

Safety variables

Adverse events, vital signs (body temperature, blood pressure, heart rate), physical examination and clinical laboratory parameters (biochemistry and haematology).

Pharmacodynamic (PD) and tentative disease specific marker variables

- MxA (protein) concentration in whole blood samples from baseline up to D13
- CD73 concentration in serum samples from baseline up to D6
- Potential Inflammatory Markers (IL-6 and HGF) in serum samples from baseline up to D13

Pharmacoeconomic variables

- Length of ICU stay, in terms of ICU free days at D30
- Length of hospital stay, in terms of hospital free days at D90
- Length of stay at another health care facility at D90
- Length of haemodialysis needed

6 Sample size considerations

The primary efficacy endpoint is all cause mortality at D30. Death within 36 hours from the first dose of the study treatment leads to exclusion from efficacy analysis. A sample size of 129 eligible patients for the primary efficacy analysis, with a 2:1 ratio to active (86) and placebo (43), will detect the difference of 22% between the two treatment groups with 80 % power using 2-sided z-test with 0.05 significance level. To take account of the planned interim analysis, calculations assume that 2 sequential tests are made (in addition to final analysis) and the O'Brien-Fleming spending function is used to determine the test boundaries. Statistical analysis plan for the interim analyses will be presented in a separate document.

Power calculation assumes 37 % proportion of events on placebo group and 15 % proportion for the active treatment group.

To achieve a sample size of 129 for the primary efficacy analysis, taking account the estimated amount of early deaths within 36 hours from first dose of the study treatment (estimated 15 %), there should be 152 patients randomised to the study.

Study was discontinued after the first Interim analysis. Therefore, the sample size did not reach the 129 patients aimed for.

7 Statistical hypotheses

The primary objective of this study is to evaluate the safety and the efficacy of FP-1201-lyo over placebo on reducing all-cause mortality at study day 30, i.e., the null-hypothesis to be tested is

H_0 : FP-1201-lyo is not superior to control with respect to all-cause mortality at study day 30

against

H_1 : FP-1201-lyo is superior to control with respect to all-cause mortality at study day 30

8 Analysis datasets

Statistical analyses will be performed on the following analysis datasets.

The Full Analysis Set for Efficacy (FAS-E) consists of all randomised patients receiving study treatment but excluding the early deaths (within 36 hours from first dose of study treatment) and comprises the analysis set on which the primary efficacy analysis is based.

The Per Protocol Set (PPS) consists of the patients in the FAS-E excluding patients with major protocol violations possibly affecting the primary study endpoint analysis.

The precise definition of the PPS at the patient level was planned to be identified at the blind review conducted both before the second interim and final analysis. The detailed criteria for patient classification will be prepared before database lock. Subject classification was to be created first for the subjects included in the second interim analysis, and later amended for the final analysis with the subjects that were not included in the interim analysis.

The first Interim analysis (after 35 evaluable patients) was based on FAS-E dataset. No classification for PPS was done for the first Interim analysis.

Statistical analyses for efficacy, PD, tentative disease specific markers and pharmacoeconomic variables are performed on both the FAS-E and PPS.

Study was discontinued after the first interim analysis. Subject classification document defining the analysis datasets in detail will be prepared and signed before database lock.

The Full Analysis Set for Safety (FAS-S) consists of all randomised patients receiving study treatment and comprises the analysis set on which the evaluation of safety is based. All safety analyses are performed on the FAS-S analysis dataset.

9 General statistical considerations

Summary statistics will include at least the number of subjects, mean, standard deviation, median, minimum and maximum for continuous variables, and frequencies and percentages for categorical variables. All data collected will be listed by subject.

In the statistical analyses a p-value less than 0.05 will be considered as an indication of statistical significance. If not stated otherwise, all tests will be performed as two-sided tests and two-sided 95% confidence intervals will be produced. Missing values will not be imputed in the analyses.

9.1 Adjustment for covariates

The primary model will include the stratification factors (age group and gender) used in the randomisation as covariates.

9.2 Handling of drop-outs or missing data

Missing values will not be imputed. Primary endpoint is mortality at Day 30 and all evaluable patients will be included in the primary analysis.

9.3 Interim analyses and data monitoring

Two Interim analyses were planned for the study with futility and efficacy stopping criteria using O'Brien-Fleming boundaries.

Study was discontinued after the first interim analysis.

9.4 Multicenter studies

Handling of centers was to be defined before second interim analysis when there would be better understanding of the center size.

Study was discontinued after the first interim analysis. Patient accrual to the different study centers was varying in amounts. Center info will not be used directly in the analyses, but country and site will be included in the tabulations of patient demographics.

9.5 Multiple comparison/multiplicity

There is one primary efficacy variable in the primary hypothesis of this study; all-cause mortality at D30. The primary evaluation of this hypothesis will be based upon the FAS-E dataset. This in itself will not give reason to adjustments for multiple comparison/multiplicity.

However, two interim analyses were to be performed after reaching 35 and 84 evaluable patients for the primary efficacy variable. For this reason, the primary efficacy endpoint was to be evaluated using O'Brien and Fleming criteria controlling the type I error rate. Using the O'Brien-Fleming spending function on the two sequential tests will cause the nominal alpha level for the primary efficacy variable in final analysis to be 0.04664. Therefore, for the primary efficacy variable a p-value less than 0.04664 will be considered as statistically significant.

As the study was discontinued after the first interim analysis, the planned O'Brien and Fleming correction will not be applied to the primary analysis. Instead, the standard p-value of less than 0.05 will be considered statistically significant.

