12.1.1 Primary efficacy variables

Primary efficacy variable is the all-cause mortality at D30. The primary efficacy analysis will be conducted using logistic regression model for the observed mortality rates in the two treatment groups. Stratification factors sex and age used in the randomisation will be included in the model. Primary result will be presented as an adjusted odds ratio and a 95% CI for the adjusted odds ratio. Also, a 95% exact unconditional confidence interval (CI) for the difference in the observed mortality rates will be calculated. As a sensitivity analysis, unadjusted results will also be presented.

For the primary comparison, a p-value less than 0.04664 was planned to be considered as statistically significant due to O'Brien-Fleming alpha spending used for the Interim analyses. Due to the study discontinuation after the first Interim analysis, two-sided significance level of 0.05 will be used for all analyses.

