13.3 Other safety variables

Other safety variable to be analysed are vital signs (body temperature, blood pressure, heart rate) and physical examination.

Vital signs data is summarized by treatment groups separately at D0, D1, D2, D3, D4, D5, D6, D9, D13 and D30. Absolute values and changes from baseline are both summarized. In addition, the maximum change from baseline over the 30-day follow-up period will be calculated for each patient and summarized. Vital signs summaries will be in terms of mean, median, SD, minimum and maximum.

Physical examination covering all the major organ systems will be performed at screening and D30. These will be summarized by treatment groups and visits using frequency and percentage of normal/abnormal observations. In addition, shift tables will be provided describing the change from screening to D30.

14 Completion and premature discontinuation

Completion and premature discontinuation will be listed. The reasons for premature discontinuation will be presented.

15 Deviations from the analyses planned in the study protocol

Study was discontinued after the first Interim analysis. Due to the early discontinuation, the planned O'Brien and Fleming correction will not be applied to the primary analysis. Instead, the standard p-value of less than 0.05 will be considered statistically significant.

Due to low number of accrued patients, the center effect was not further explored in the analyses. Analysis of study centers was limited to summary statistics for baseline information.

Due to the early discontinuation of the study, the pharmacoeconomic endpoints (see section 12.3.2) will not be analysed.

There are no other major deviations in the statistical analysis plan from the analyses planned in the study protocol.

16 Execution of statistical analyses

Statistical analyses will be performed by [REDACTED].

17 Hardware and software

[figure not shown]
Statistical analysis, tables and patient data listings will be performed with SAS[®] version 9.4 or later for Windows (SAS Institute Inc., Cary, NC, USA).

18 References

Clinical Study Protocol (FP1CLO006), Final Protocol version 05 (16 April 2019), Faron Pharmaceuticals Ltd.

19 Appendices

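### Does testing the primary endpoint at p<0.05, a level set after the first interim analysis, inflate the type I error?

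*SAP*

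**What the plan says.** Protocol section 8.6 commits the primary endpoint to O'Brien-Fleming criteria with looks at (at least) 31 and 84 evaluable patients. It describes the first look as mainly a futility look, brought forward because recruitment had stagnated. SAP section 9.5 gives the looks as 35 and 84, with a final nominal level of 0.04664.

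The current SAP was written after the first look. Section 8 records that "The first Interim analysis (after 35 evaluable patients) was based on FAS-E dataset", and protocol section 5.4 says the randomisation code would be opened for it. On the outcome, SAP section 9.3 says only: "Study was discontinued after the first interim analysis".

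The new threshold appears in three places:

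- Section 9.5: "Instead, the standard p-value of less than 0.05 will be considered statistically significant".
- Section 12.1.1, which recalls that "a p-value less than 0.04664 was planned to be considered as statistically significant" and then says: "Due to the study discontinuation after the first Interim analysis, two-sided significance level of 0.05 will be used for all analyses".
- Section 15 (deviations from the protocol), which lists that the planned "Fleming correction will not be applied to the primary analysis".

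Section 2 nevertheless says: "The analysis plans concerning the primary analyses are not changed from the previous version". The futility criteria are not in either document; SAP section 6 says: "Statistical analysis plan for the interim analyses will be presented in a separate document".

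**The concern.** A significance threshold for the primary mortality endpoint was relaxed after an interim analysis for which the code was to be opened, and discontinuation is the only justification. Discontinuation alone does not make 0.05 valid; that depends on why the trial stopped. If it stopped for futility or slow recruitment, almost no alpha had been used and a test at 0.05 is sound. If it stopped because the first look was encouraging but had not crossed the boundary, then 0.05 applied to the same patients is in effect an early efficacy claim at a level far looser than planned.

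Protocol section 9.9 lets the sponsor stop at any time on new efficacy information, so the second route is not formally closed. A reader with a primary p-value just under 0.05 might then be unsure what error rate it carries. The sentence in SAP section 2 adds to the unease, because it sits badly with sections 9.5 and 12.1.1.

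**Working it through.** **Inputs.** Two-sided alpha 0.05, 129 evaluable patients and O'Brien-Fleming spending (SAP section 6); looks at 35 and 84 (SAP section 9.5). The information fractions are 35/129 = 0.271, 84/129 = 0.651 and 1.

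**1. Reproduce the planned level.** Use Lan-DeMets O'Brien-Fleming-type spending with 0.025 per side: α(t) = 2[1 − Φ(2.2414/√t)].

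- At t = 0.271, α = 0.0000168 per side, or 0.000034 two-sided. The boundary is |Z| > 4.147.
- The later boundaries are 2.545 and 1.990. The final nominal p is 0.0466, and 0.04664 if the second fraction is rounded to 0.65. This matches the SAP.
- With only the 35-patient look before a last analysis, the level left is 0.04999. For a stop unrelated to the results, 0.05 is therefore right, with 2.5% in the benefit direction.

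**2. Futility stop.** Suppose the trial stops if Z1 < c and is then tested at |Z| > 1.96 on the same patients; otherwise it continues with the planned boundaries. For any c below 1.96 a stopped trial cannot be significant for benefit, so false benefit can only fall below the planned 2.5%. The documents give no value of c, so a range is assumed.

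| c | False benefit | False harm | Two-sided |
|---|---|---|---|
| −1.5 | 2.5% | 4.0% | 6.5% |
| −1.0 | 2.5% | 3.4% | 5.9% |
| −0.5 | 2.4% | 3.0% | 5.4% |
| 0 | 2.3% | 2.7% | 5.0% |
| 0.5 | 2.0% | 2.6% | 4.6% |
| 1.0 | 1.6% | 2.5% | 4.1% |

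The two-sided total passes 5% only for c below 0, and only through the harm direction. The SAP's alternative hypothesis (section 7) is superiority of FP-1201-lyo, so the error at stake is false benefit, which never exceeds 2.5%.

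**3. Off-plan favourable stop.** Suppose the trial stops if Z1 > c and is tested at 1.96; otherwise it continues as planned.

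- c = 1.96: 2.5% at the first look plus 2.0% from later looks gives 4.5% false benefit. Adding 2.5% for harm gives 7.0% two-sided.
- c = 1.5: 4.0% and 6.5%.
- c = 1.0: 3.5% and 5.9%.
- A symmetric rule, |Z1| > 1.96: 4.5% and 8.9%.

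**4. Planned efficacy stop.** A result beyond |Z| = 4.147 also meets 0.05, so nothing changes.

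**5. Effect of moving from 0.04664 to 0.05.** All tables of deaths were enumerated for 35 patients split 22:13, 23:12 and 24:11. None has an unadjusted pooled-z p-value in the interval from 0.04664 to 0.05. The same holds for the unadjusted Wald logistic test, leaving out tables with a zero cell, where it cannot be computed.

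**The case for a change.** The strongest case for acting is that the primary threshold was changed after the interim, that protocol section 8.6 states what the first look was for and not what it found, and that the one fact on which validity depends is missing. On that view 0.05 should be allowed only if a futility or unrelated stop is documented. The arithmetic for the unfavourable route is correct, and the omission is real.

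The remedy does not follow, for four reasons.

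- The harmful route needs a sponsor to have stopped on a promising result that missed the boundary. Everything the documents do say about this look points to futility and poor accrual. Protocol section 9.9 is a general right to terminate that also lists slow enrolment.
- This SAP was written after the stop, so the reason was already known. A conditional rule would branch on a settled fact.
- Such a rule would misfire after a safety stop. Under protocol section 9.8 the IDMC reviews serious adverse events unblinded, and deaths are among them. A harm-driven stop would therefore not count as unrelated to unblinded mortality, yet false benefit would not be inflated.
- The interim analysis plan, the SAP dated 17.6.2019 and the study report were not available. Silence in this SAP does not show that the reason is undocumented.

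What stands is that a sentence giving the reason for stopping would help the reader. Protocol section 8 already requires deviations from the SAP's planned analyses to be justified in writing in the final clinical study report, which is a natural place for it.

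**Conclusion.** No change to the plan follows. On the routes the documents point to (futility or stagnated recruitment), testing at 0.05 holds false benefit at or below 2.5%, as planned. The inflation to about 3.5% to 4.5% belongs to a favourable off-plan stop that nothing in the documents indicates. The step from 0.04664 to 0.05 changes no conclusion in any unadjusted table that could be tested, and it is disclosed in SAP sections 9.5, 12.1.1 and 15. The missing stop reason is a gap that the study report can fill. The sentence in section 2 is loose wording, and those three sections keep it from misleading anyone.

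This rests on assumed stopping thresholds, since none is given; on a normal approximation that is rough at 35 patients; and on the final test using the 35 interim patients. If a few more patients enter the final data (totals of 38 to 50 were tried), false benefit after a futility stop at thresholds of 0 to 1.0 stays below 2.5%. The adjusted model in section 12.1.1 could not be enumerated without the strata counts.
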